4.6 Intervention Checklist

"Tick Box" items will be entered into SPSS and analysed by:

1. Describe the number (percentage) of use of each box ticked "yes" or "No"

2. Describe numbers for "woman was able to remove pessary" and "woman was able to re-insert pessary"

3. Crosschecking of "woman was able to remove pessary" and "woman was able to re-insert pessary" with 2 week follow-up phone call to see if women who successfully removed and re-inserted pessary during teaching sessions are more likely to have successfully removed, re-inserted and positioned pessary at home.

Free text comments from HCP will be coded using a coding framework developed using content analysis and their frequency noted. Discussions of these and descriptive statistics will be used to decide if the delivery of the self-management teaching will need to be amended after the pilot study.

4.7 2 week follow-up phone call CRF

The analysis mainly focuses on fidelity of intervention delivery and clinical acceptability. Additionally we will be monitoring how many women are transferring back to standard care after being randomised to self-management.

"Tick Box" items will be entered into SPSS and analysed by:

- Describe number of women who successfully removed, re-inserted and positioned own pessary within 2 weeks after initial teaching session
- 2. Describe number of additional follow-up calls arranged
- 3. Describe number of additional training sessions arranged

4.8 Main Trial Questionnaires

The trial statisticians, blinded to the process evaluation data but unblinded to trial results, will undertake a statistical mediation analysis to investigate the extent to which any observed effect of self-management on women's quality of life (measured using PFIQ-7 at 18 months) is mediated by self-efficacy. Single-mediator models will individually assess the General Self-Efficacy scale and all items from pessary confidence questionnaire as potential mediating factors. The mediation analysis will use a regression-based modelling framework, with separate regression models to estimate direct effects. Indirect effects will be derived from the direct effects, with confidence intervals using Sobel's method (Sobel, 1982). This regression modelling framework will be extended to incorporate linear mixed models, specified consistently with the modelling strategy outlined in the statistical analysis plan. This will ensure the process evaluation researchers remain blinded to trial results until the appropriate time.

In addition, question 8 in the pessary use questionnaire is an open ended question and will be analysed using content analysis. A similar approach will be taken to all other free text comments provided in completed questionnaires.

5. Data synthesis across data sources and triangulation

Data synthesis will focus on the research questions where there is crossover between different data sources. The synthesis will be developed as follows (O'Cathian et al, 2010):

- 1. All 'findings' for each research question will be re-read.
- 2. A matrix was developed that outlines the data sources and the relevant research question.
- 3. Each source data will be summarised in the appropriate cell (cells remain blank if there is no data from that data source).
- 4. The agreement/ disagreement across sources will be documented in the final column.
- **5.** A summary of key findings outlining explanation and meaning for each concept will be documented.

References

Sobel, M. E. (1982). Asymptotic confidence intervals for indirect effects in structural equation models. *Sociological Methodology*, *13*, 290-312.

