Manchester University

University for the Common Good

Process Evaluation

Analysis Plan

FINAL Version 1.0

16 March 2021

 Date: 27 th April 2021
 Date: 27 th April 2021

Glossary of abbreviations

DMEC Data Monitoring and Ethics Committee HTA Health Technology Assessment NIHR National Institute for Health Research PMG Project Management Group TOPSY **T**reatment **O**f **P**rolapse with **S**elf-care pessar**Y** TSC Trial Steering Committee RCT Randomised Controlled Trial

1. Introduction

The NIHR HTA commissioning brief asked for an internal pilot study "to demonstrate the ability to recruit and randomise, and participants' adherence to allocated treatment, with clear stop/go criteria to the main trial". This document sets out how the process evaluation data will be collected, analysed and reported. Quantitative data where referred to will be analysed in line with the conventions laid out in the main trial Statistical Analysis Plan (SAP) except where stated otherwise.

TOPSY includes a nested process evaluation which runs alongside the main RCT. The process evaluation will collect and analyse qualitative and quantitative data about recruitment, intervention fidelity, participants' experiences of participating in the trial and adherence to trial protocols and group assignment. Findings will be reported to PMG, TSC, DMEC and HTA.

2. Our definition of 'on treatment'

For women self-managing their pessary, 'on treatment' is;

- If they are randomised to self-management;
- IF they have NOT discontinued pessary care (determined by the change of status form);
- If they have received the intervention;
- AND if they have answered Yes to question 2d (Pessary use questionnaire) "Have YOU inserted your pessary yourself in the last 6 months" at either 6,12 or 18 months"

For women in the standard clinic-based care arm of the study,

"On treatment" is:

- IF they are randomised to standard care;
- IF they have NOT discontinued pessary care (determined by the change of status form);
- AND if they have answered Yes to question 1 (Pessary use questionnaire) "Have you used a pessary for prolapse at any time in the last 6 months?" at least once at either 6, 12 and 18 months
- AND they have ticked NO to Q2d (Have you inserted your pessary in the last 6 months) at ALL time-points (6 12 and 18 months).

** Additional analysis – those who have answered yes to q2d at any time point who are in any group (standard care and self-management)

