3.2 Types of data

- 1. Audio-record self-management teaching sessions (21 audio-recordings)
 - 1-2 per centre
 - Time frame: June 2018 February 2020
- 2. Audio-record 2-week follow-up phone calls (34 audio-recordings)
 - 1-2 per centre
 - Time frame: June 2018 March 2020
- 3. Interviews with healthcare professionals (HCPs) (35 telephone interviews)
 - Recruiters (1 per centre) and healthcare professionals delivering the intervention (1 per centre); only 1 interview where HCP holds dual roles as recruiter and intervention deliverer
 - Time frame: August 2018 February 2020
- Interviews with randomised women (36 face-to-face interviews baseline (18 self-management, 18 standard care); and 23 18-month follow-up) and non-randomised women (20 telephone baseline interviews; and 18 18-month follow-up)

Time frame: August 2018 – April 2021

- 5. Intervention checklist, CRF 05 (n=156)
- 6. 2-week follow-up call, CRF 06 (n=145)
- 7. Main trial Questionnaires (340 women randomised at baseline)

4. Analysis method for each data source

The process evaluation researchers are blinded to all trial data, including the analysis element of this; however, they are unblinded for all qualitative process evaluation data to which the trial team is blinded.

Each data source will be analysed individually in the first instance to reach separate conclusions and findings then synthesised across data sources. All qualitative data sources will be transcribed verbatim and entered into NVivo for data management. All of the analysis described below will be undertaken by the process evaluation subgroup of grant-holders. Analysis will not be shared with the wider grant-holding group until the main trial findings are revealed.

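### Sobel intervals for the indirect effects have unbalanced tails, and exclude zero less often than a Monte Carlo interval, when both mediation paths are small to moderate

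*SAP*

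**What the plan says.** Section 4.8 plans a mediation analysis of the effect of self-management on quality of life, "measured using PFIQ-7 at 18 months". Mediators are taken one at a time: "Single-mediator models will individually assess the General Self-Efficacy scale and all items from pessary confidence questionnaire as potential mediating factors". Separate regressions estimate the paths. For the indirect effects the plan states: "Indirect effects will be derived from the direct effects, with confidence intervals using Sobel's method (Sobel, 1982". It adds: "This regression modelling framework will be extended to incorporate linear mixed models".

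No bootstrap, Monte Carlo or other interval is named, either as the main method or as a sensitivity analysis. Section 1 says that quantitative data "will be analysed in line with the conventions laid out in the main trial Statistical Analysis Plan (SAP) except where stated otherwise". The interval is stated here, so the main trial SAP, which is not at hand, would not override it.

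Section 3.2 gives the number of women: "Main trial Questionnaires (340 women randomised at baseline". The plan gives no number analysable at 18 months, no expected path sizes, and no confidence level or significance rule for mediation.

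**The concern.** Naming Sobel's method implies that the indirect effect is the product of two estimates: a (arm to mediator) and b (mediator to PFIQ-7, adjusted for arm). A product of two normal estimates is not normal. If both are only a few standard errors from zero, the product is skewed away from zero. Its estimated standard error also moves with the estimate: when the product comes out small, so does the standard error. A symmetric interval then falls too often on the zero side of the truth.

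The stated aim is to measure how far self-efficacy explains any effect, so the interval limits matter even without a formal test. They would feed the cross-source synthesis in section 5. An interval that spans zero because of its construction could be read there as a lack of support for self-efficacy as a mechanism.

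**Working it through.** The plan has no figure to reproduce for this analysis, so the check is a simulation with stated assumptions.

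**Inputs from the plan:** Sobel's method, single-mediator regressions and PFIQ-7 at 18 months (section 4.8); 340 randomised (section 3.2).

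**Assumed:** two-sided 95% intervals; 1:1 allocation; 340 women analysed (no loss), 290 (about 85%) or 270 (about 20% loss); normal errors with residual SD 1; path sizes as listed.

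**Formulas**
- Sobel: ab ± 1.96 × √(a²·SE_b² + b²·SE_a²).
- Monte Carlo: draw a* from N(a, SE_a²) and b* from N(b, SE_b²) independently, and take the 2.5th and 97.5th percentiles of a*b*.

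**One worked case: 340 women, estimates a = 0.3 and b = 0.14**
- SE_a = √(4/340) = 0.1085, so a/SE_a = 2.77.
- SE_b ≈ 1/√340 = 0.0542, so b/SE_b = 2.58.
- ab = 0.042.
- Sobel SE = √(0.09 × 0.00294 + 0.0196 × 0.01176) = √0.000495 = 0.0223.
- Sobel interval: 0.042 ± 0.0436, that is −0.002 to 0.086.
- Monte Carlo interval, from the same four numbers: 0.006 to 0.094.

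Each path is more than 2.5 standard errors from zero, yet the Sobel interval includes zero. For independent normal estimates the third central moment of the product is 6ab·SE_a²·SE_b², and its variance is a²SE_b² + b²SE_a² + SE_a²SE_b². The skewness here is therefore about 0.71; simulation gives 0.75.

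**How often the interval excludes zero, small-to-moderate paths (8,000 simulated trials per row)**

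| Women | a | b | Sobel | Monte Carlo | Difference (points) |
|---|---|---|---|---|---|
| 290 | 0.3 | 0.15 | 29% | 50% | 21 |
| 290 | 0.3 | 0.20 | 49% | 67% | 18 |
| 290 | 0.4 | 0.20 | 73% | 86% | 13 |
| 340 | 0.3 | 0.15 | 40% | 61% | 21 |
| 340 | 0.3 | 0.20 | 61% | 75% | 14 |
| 340 | 0.4 | 0.20 | 84% | 92% | 8 |

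**Stronger paths**

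| Women | a | b | Sobel | Monte Carlo |
|---|---|---|---|---|
| 290 | 0.5 | 0.3 | 97.7% | 98.4% |
| 290 | 0.8 | 0.2 | 91.2% | 91.5% |
| 340 | 0.3 | 0.39 | 76.3% | 79.7% |
| 340 | 0.8 | 0.14 | 72.4% | 76.2% |
| 340 | 0.5 | 0.39 | 99.5% | 99.7% |

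**Tails and coverage, 340 women (4,000 trials per row; simulation error at most about 0.8 points)**

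| a | b | Sobel wholly below / above truth | Sobel coverage | Monte Carlo wholly below / above truth | Monte Carlo coverage |
|---|---|---|---|---|---|
| 0.3 | 0.14 | 7.1% / 0.5% | 92.3% | 4.1% / 1.1% | 94.8% |
| 0.3 | 0.20 | 6.1% / 0.7% | 93.1% | 3.7% / 1.8% | 94.5% |
| 0.4 | 0.20 | 6.5% / 0.6% | 92.9% | 3.2% / 1.1% | 95.7% |
| 0.5 | 0.39 | 4.0% / 1.3% | 94.7% | 2.6% / 1.8% | 95.5% |

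With 270 women, a = 0.3 and b = 0.14, Sobel misses 7.9% below and 0.4% above (coverage 91.7%).

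**No mediation (one path zero), 340 women:** with a = 0 and b = 0.14, Sobel excludes zero in 0.9% of trials and Monte Carlo in 2.9%. With a = 0 and b = 0.39 the figures are 4.7% and 6.1%.

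**Point estimate:** the bias of ab is at most 0.0015 in every scenario.

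Mixed-model clustering and ordinal confidence items were not simulated.

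**The case against.** The strongest reply is that the loss comes from weak paths, not from the size of the trial, and that the plan gives no path sizes. Teaching women to handle their own pessary could shift some pessary-confidence items a good deal, and then the choice of interval hardly matters. This stands. A reader might infer that 340 women are simply too few for Sobel's method; the second table shows otherwise. Equally, nothing in the plan shows that every mediator has a strong path, and the same method is fixed for a general scale and for each single item.

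Second, a reader might infer that Sobel is strongly conservative whenever there is no mediation. That holds only when the non-zero path is weak; with a strong one its error rate approaches 5%.

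Third, a reader might infer that the plan will declare mediation absent. It states no significance rule or decision for the indirect effect, so how often zero is excluded describes the interval and not a planned test. Coverage of 91 to 94% is a moderate shortfall.

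Fourth, the alternative is not perfect. Its tails are also uneven, though less so, and it can slightly exceed 5% at one kind of null. A percentile bootstrap was tried only with a skewed outcome and independent women (290 women, 1,000 trials). It excluded zero in 48% against Sobel's 30%, 65% against 46%, and 83% against 71%, in the three path settings of the first table. Whether resampling women within arm suits the planned mixed models cannot be judged without the main SAP.

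**Conclusion.** The point holds conditionally. Section 4.8 fixes a single interval that fits a product of coefficients poorly when both paths are small to moderate. For a = 0.3 to 0.4 and b = 0.15 to 0.20, with 290 to 340 women:
- the tails are about 6 to 8% against under 1%;
- coverage is about 91 to 94%;
- zero is excluded about 8 to 21 points less often than with a Monte Carlo interval.

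The difference shrinks to between 0 and about 4 points once a path is strong. The documents do not support calling the estimated indirect effect biased or mis-centred: only the interval is misplaced. These sizes rest on assumed paths, 1:1 allocation, 95% intervals and independent normal errors. This is a secondary analysis and no main trial conclusion depends on it. The change is worth making because the path sizes are not known in advance and the better interval costs almost nothing.

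**What to change.** Replace the Sobel clause in section 4.8 with wording such as:

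*The indirect effect is the product of the arm-to-mediator coefficient and the mediator-to-PFIQ-7 coefficient adjusted for arm. Its confidence interval is the Monte Carlo interval: both coefficients are drawn independently from normal distributions with the estimated means and standard errors, and the 2.5th and 97.5th percentiles of 20,000 products are reported. The seed is recorded.*

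The percentiles assume a 95% level and should follow the main SAP if it sets another. The method needs only the two estimates and their standard errors, so it applies directly to the linear mixed models. A percentile bootstrap is an alternative if the resampling respects the clustering in those models. Sobel's interval can be kept as a secondary result for comparison.

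Cost: one sentence and a few lines of code, with no new data. Downsides: the limits depend on random draws, hence the fixed seed and number of draws, and the error rate can be at or slightly above 5% (about 5 to 6%) when one path is zero and the other strong.
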